## 5 STUDY DESIGN

### 5.1 Description of the study design

This is a non-interventional, multicentre, prospective study for patients with highly active relapsing MS for whom Cladribine 10 mg tablets therapy was indicated independently before enrolment to the study. It is planned to enrol about 100 patients in 12 sites specialized for MS treatment in Slovakia (for sample size consideration please see Section 12.1).

Eligible subjects will undergo all visits and procedures before and during the treatment as per local standards and Cladribine 10 mg tablets administration will be in accordance with approved SmPC. There is no assessment mandated per study protocol. Management of disease including administration of rescue therapy and visit schedule are fully at the treating physician's discretion. Data for the study will be extracted from medical charts and entered into the electronic Case Report Forms (eCRF). Study assessments schedule (Table 8-1: Flow chart) is approximate, all described assessments and events will be collected and finally statistician will analyse them within relevant window for respective visit. According to standard practice in Slovakia, patients treated by DMD visit their physician at MS centre at least once per year (as required by payers) but usually every 3 months.

To collect high quality adherence data, patients will be asked to bring used/partially used Cladribine 10 mg tablets packages to the next visit after dosing and physicians will record number of actually used tablets, if Cladribine 10 mg tablets are not administered in the participating site as per standard practice.

Patients will be followed up to 4 years after the first dose of Cladribine 10 mg tablets. Patients with low lymphocyte count to start Cladribine 10 mg tablets therapy after the first year are allowed to postpone second cycle up to 6 months until lymphocyte count recovers (as per SmPC) and therefore their participation may take up to 4.5 years.

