### 6.3.3 Withdrawal Criteria

- Withdrawal of patient consent
- Start of a new disease modifying drug
- Lost to follow-up

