### 7.2 Secondary endpoints

- Proportion of relapse-free patients at 24 and 48 months
- ARR at 24 months
- The time to sustained progression of disability from baseline up to 24 and 48 months
- Time to the first relapse from baseline up to 48 months
- Time to the second relapse from baseline up to 48 months

- Changes in mean number of T1 Gd+ lesions per MRI scan taken at 12, 24, 36 and 48 months compared to baseline
- Changes in mean number of active T2-weighted lesions per MRI scan taken at 12, 24, 36 and 48 months compared to baseline
- Changes in level of disability as measured by EDSS at 6, 12, 18, 24, 30, 36, 42 and 48 months compared to baseline
- No evidence of disease activity (NEDA-3) at 24 and 48 months
- The proportion of patients receiving rescue therapy according to local standards of care from baseline up to 48 months
- Patient adherence to Cladribine 10 mg tablets treatment after both dosing periods as assessed at 3 and 15 months (by counting used tablets from original packages as patients will be asked to bring them to the site).
- Frequency of adverse events interviewed or reported spontaneously by the patients or as noted on physical, MRI or laboratory examinations up to month 48
- Percentage of patients with at least 1 Common Terminology Criteria for Adverse Events (CTCAE) grade 3 or 4 Lymphocyte Toxicity up to month 48
- Median time to recovery from grade 3 or 4 Lymphocyte Toxicity
- Percentage of patients who developed herpes zoster infections or malignancies up to month 48

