- Concomitant medication (only corticosteroids, myorelaxants, analgesics, antidepressants, anxiolytics) from the last visit

**V10 - Visit Month 7 Year 4** (30 months after the first dose of Cladribine 10 mg tablets in Year 2)

- Visit date
- EDSS score
- Any relapse and rescue therapy from the last visit
- Any AE from the last visit
- Concomitant medication (only corticosteroids, myorelaxants, analgesics, antidepressants, anxiolytics) from the last visit

**EOS - Visit Month 12 Year 4** (36 months after the first dose of Cladribine 10 mg tablets in Year 2)/Premature Withdrawal Visit

- Visit date
- MRI status
- EDSS score
- Any relapse and rescue therapy from the last visit
- Any AE from the last visit

Concomitant medication (only corticosteroids, myorelaxants, analgesics, antidepressants, anxiolytics) from the last visit

Table 8-1: Flow chart

Year	Year 1			Year 2			Year 3		Year 4		
	pre-dose	3	7	pre-dose	3	7	1	7	1	7	12
Timing (month if applicable)	V1	V2	V3	V4	V5	V6	V7	V8	V9	V10	EOS /PW*
Informed consent	X										
Inclusion/Exclusion criteria	X										
Baseline characteristics (patient and disease)	X										
Patient weight	X			X							
Is patient eligible to start Cladribine 10 mg tablets therapy?	X			X							
MRI status	X			X			X		X		X
Lymphocyte count (or Blood count)	X	X	X	X	X	X					
Number of Cladribine 10 mg tablets to be used	X			X							
Date of Cladribine 10 mg tablet therapy start and number of Cladribine 10 mg tablets really used (as counted from original packages brought back to the site)		X			X						
EDSS	X		X	X		X	X	X	X	X	X
Any relapse and rescue therapy from the last visit		X	X	X	X	X	X	X	X	X	X
Any AE from the last visit		X	X	X	X	X	X	X	X	X	X
Concomitant medication (only corticosteroids, myorelaxants, analgesics, antidepressants, anxiolytics) from the last visit		X	X	X	X	X	X	X	X	X	X
Reasons for premature withdrawal, if applicable											X

\*PW – Premature Withdrawal Visit in case of patient premature withdrawal

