### 12.2 Data Analysis

Analysis of collected data is based on descriptive statistics including absolute and relative frequencies of discrete variables. Continuous variables are described by count (without missing), mean and its 95% confidence interval (CI), standard deviation, median, minimum, and maximum. Discrete variables are described by count (absolute frequency), and percentages (relative frequency).

Missing data will not be replaced.

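### EDSS change is summarised at eight time points from whoever has a value; if worsening patients leave, later means look too favourable, and a repeated-measures model is a cheap but conditional improvement

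*Protocol*

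**What the plan says.** **Endpoint.** Protocol section 7.2 lists "Changes in level of disability as measured by EDSS at 6, 12, 18, 24, 30, 36, 42 and 48 months compared to baseline" among the secondary endpoints. The same section lists time to sustained progression of disability separately.

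**Method.** Section 12.2 opens with "Analysis of collected data is based on descriptive statistics including absolute and relative frequencies of discrete variables". For continuous variables it gives "Continuous variables are described by count (without missing), mean and its 95% confidence interval (CI), standard deviation, median, minimum, and maximum", and it closes with "Missing data will not be replaced". The Protocol Summary repeats these rules. No longitudinal model is named.

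**Leaving the study.** Section 6.3.3 lists withdrawal of consent, "Start of a new disease modifying drug" and "Lost to follow-up".

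**EDSS at leaving.** In the flow chart (Table 8-1) the last column serves both as end of study and as premature withdrawal ("PW – Premature Withdrawal Visit in case of patient premature withdrawal"), and EDSS is marked in it. However, section 5.1 states "There is no assessment mandated per study protocol", so that value can be absent. The protocol does not say whether a withdrawal EDSS is summarised with the month-48 values.

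**Route for change.** Section 12 says a statistical analysis plan (SAP) will be built from this part of the protocol, with changes of method described and justified there. It names IBM SPSS as the software.

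**The concern.** A mean of available values estimates the mean of the enrolled cohort only if being absent is unrelated to EDSS. Section 6.3.3 makes that hard to take for granted. The cohort is selected for highly active disease, and continued disease activity is a foreseeable reason to start another DMD, which ends participation. A patient whose EDSS was rising before leaving contributes to the earlier means and to none of the later ones, although the rising values stay in the database.

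Absence need not come from withdrawal alone. Section 5.1 describes visits at least once a year, usually every three months. A patient seen only yearly may lack some half-yearly EDSS values, so the composition of the eight means can also vary among patients who stay.

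At stake is how the course of EDSS over four years is read: worsening in the cohort could appear smaller than it is.

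**Working it through.** **The plan's own figure.** The protocol gives no EDSS mean, SD or drop-out mechanism. The only stated figure used here is the drop-out allowance in section 12.1: 85 / (1 − 0.15) = 100. It reproduces.

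**Set A: exit depends on the last recorded EDSS change.** Assumed, not from the protocol: 100 patients, eight half-yearly visits, mean change +0.15 at month 48, patient slope SD 0.25 per year, visit SD 0.5. After each visit, patients with a rise of at least 1 point leave with one probability and all others with a lower one. Bias = available-case mean − full-cohort mean. The model estimate is the maximum-likelihood mean with unstructured covariance.

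| Dependence (exit per interval) | Drop-out | Full cohort | Available cases | Model | Bias |
|---|---|---|---|---|---|
| Strong (20% vs 0.4%) | 14.3% | 0.143 | −0.011 | 0.146 | −0.011 − 0.143 = −0.154 |
| Weak (5% vs 1.8%) | 13.5% | 0.143 | 0.117 | 0.143 | 0.117 − 0.143 = −0.026 |

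A repeat of the strong case with 1,000 runs gave 0.148 and −0.004, a bias of −0.152. An intermediate case (10% vs 1.3%, 14% drop-out) gave a bias of about −0.07.

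**Precision under Set A.** SD of change at month 48 = √((0.25 × 4)² + 0.5²) = √1.25 = 1.118. With 100 patients the half-width is 1.96 × 1.118 / √100 = 0.219. With 86 patients and the same SD it would be 0.236, but selective exit trims the largest changes, so about 0.22 is a fair working value. The strong-case bias is 0.15 / 0.22, about two-thirds of the half-width.

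**Set B: gradual worsening with larger assumed changes.** Mean slope 0.05 or 0.10 per year (true month-48 change 0.20 or 0.40), slope SD 0.25 or 0.35, odds of leaving multiplied by 2.7 or 7.4 per EDSS point, 15% drop-out.

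| Exit driven by | Bias, available cases | Bias, model | Share removed |
|---|---|---|---|
| Nothing related to EDSS | about 0 | about 0 | – |
| Last recorded EDSS | −0.10 to −0.28 | about 0 | about 100% |
| EDSS not recorded | −0.12 to −0.33 | −0.04 to −0.09 | 65–75% |

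**Set C: a sudden, lasting 1-point step at which the patient leaves.** Step rate 0.06 or 0.12 per year, probability of leaving at a step 0.3 or 0.6.

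| Withdrawal EDSS in the model | Drop-out | Bias, available cases | Bias, model | Share removed |
|---|---|---|---|---|
| Yes | 5–20% | −0.05 to −0.21 | −0.04 to −0.15 | 22–33% |
| No | 6–23% | −0.06 to −0.25 | same as available cases | 0% |

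Sets A and B agree on direction. Sets B and C show that the benefit of the model depends on why patients leave and on whether their last EDSS is used.

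**The case against.** **Section 12.2 is generic and an SAP may refine it.** It does not mention EDSS, and it cannot be exhaustive, because section 7.2 has time-to-event endpoints that it does not cover. Not replacing missing data also does not rule out a mixed model, which replaces nothing. This stands as a reason for modest weight. Still, it is the only method the protocol gives for a continuous variable, and section 12 makes it the default from which departures must be justified.

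**The withdrawal visit may already capture the worsening.** This objection is substantial. In the strong Set A case, averaging month-48 values together with each leaver's last EDSS gave 0.159 against a full-cohort 0.148. But that mixes values taken at different times, does nothing for the means between exit and month 48, and depends on a record that is not mandatory and a rule that the protocol does not state.

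**The size rests on assumptions.** True. The strong case needs a 50-fold contrast in exit risk (20 / 0.4 = 50), and even then the shift lies inside the CI half-width. With weak dependence the bias is negligible.

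**The target changes.** Also true. The model estimates change as if leavers had continued without the new drug, which is not what a real-life cohort observes after a switch.

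**Readings that go too far.** A reader might infer that a repeated-measures model removes most of the bias. Set A shows this only because exit there depends on recorded EDSS, the condition under which the model works; Set C shows 0 to 33%. A reader might also infer that leavers are known to be worsening, but the protocol does not say so. Nor is EDSS change the sole four-year disability result, since time to sustained progression is its own endpoint.

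**Conclusion.** The concern holds in a limited form. The stated default reports eight means from possibly different sets of patients, and the withdrawal criterion makes exit related to worsening plausible. If it occurs, later EDSS means look too favourable. Under Set A, at about 14% drop-out, the month-48 shift runs from 0.02–0.03 points to about 0.15 points, against a CI half-width of about 0.22. The larger slopes and odds ratios of Set B give larger shifts. If leaving is unrelated to EDSS there is no bias. All EDSS inputs are assumptions.

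A repeated-measures model was no more biased than the available-case mean in any scenario with EDSS-related exit, to within simulation error, and often much less so. It is an improvement and not a cure. The weight is that of a worthwhile, cheap addition to one secondary, descriptive, single-arm endpoint. The primary annualised relapse rate is not affected by this point.

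**What to change.** In the SAP, under the route in section 12:

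1. Add a mixed model for repeated measures on all recorded EDSS changes, with visit as factor, baseline EDSS as covariate and unstructured covariance (Toeplitz if it does not converge). Enter the premature withdrawal EDSS at its actual time, in the visit window its date falls in and not as month 48. Report mean change with 95% CI at months 24 and 48.
2. Keep the planned descriptive table beside it. The number observed at each visit is already part of section 12.2; add the reasons for leaving, which Table 8-1 already collects.
3. State that the model estimates change as if leavers had continued without the new drug. State also that it removes the bias fully only if exit is explained by recorded EDSS, partly if exit depends on unrecorded gradual worsening, and little or not at all if patients leave at a sudden unrecorded step.
4. Add one not-at-random sensitivity analysis. A simple form adds δ to the model-based mean of those without a month-48 value. The overall mean then moves by (share without a value) × δ; with 15% absent and an assumed δ of 1 point, 0.15 × 1 = 0.15. This needs no imputed values.

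**Cost.** SAP text and one mixed-model procedure in the stated software, with no new data, visits or patient burden. The downside is some extra analysis work and a missing-at-random assumption, which is weaker than the one the available-case mean needs.

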### 12.1 Sample Size

A sample size of 85 subjects will have more than 80% power to achieve a supposed ARR 0.14 (95 % CI: 0.12–0.17) using a 2-sided significance level of 0.05. Assuming a 15% drop-out rate, a total of 100 patients will be targeted for this study.

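### Relapse-free and NEDA-3 status are set as plain percentages with no rule for patients who leave, so the result depends on who leaves and on an unstated denominator

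*Protocol*

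**What the plan says.** Protocol section 7.2 lists two binary status endpoints at fixed times: "Proportion of relapse-free patients at 24 and 48 months" and "No evidence of disease activity (NEDA-3) at 24 and 48 months". It gives neither a denominator nor a rule for patients who leave before the time point.

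Section 12.2 fixes one kind of summary for such variables: "Discrete variables are described by count (absolute frequency), and percentages (relative frequency". On incomplete data it says "Missing data will not be replaced".

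Four other places bear on the point:

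- Section 6.3.3 makes the start of another disease modifying drug a reason for withdrawal, alongside withdrawn consent and loss to follow-up.
- Section 12.1 plans for attrition: "Assuming a 15% drop-out rate, a total of 100 patients will be targeted for this study".
- Section 8.2 and Table 8-1 schedule relapse, EDSS and MRI at the premature withdrawal visit, while section 5.1 says that the protocol mandates no assessment.
- Section 7.2 also lists time to first relapse up to month 48. There is no time-to-event counterpart for NEDA-3.

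**The concern.** A percentage at month 48 needs a decision about each patient who left before month 48. The protocol makes none. Three plain-percentage readings are open:

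- use completers only;
- use everyone, and count leavers with no recorded event as event-free;
- use completers plus leavers with a recorded event, and drop the event-free leavers.

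These give different answers, and which one is close to the truth depends on why patients leave. The withdrawal rule on new disease modifying drugs matters here. A switch of drug plausibly follows breakthrough activity, so the design itself tends to remove patients who have already failed these endpoints. If completers are then used, known failures leave the denominator and disease control looks better than it was.

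NEDA-3 is more exposed than relapse. It also needs EDSS and MRI, which can be absent even in patients who stay, because no assessment is mandated.

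**Working it through.** **Inputs.** Section 12.1 gives 85 evaluable patients, 15% drop-out, a total of 100 and an assumed annualised relapse rate of 0.14, with interval 0.12 to 0.17. Section 5.1 gives 4 years of follow-up. A constant Poisson relapse rate, the same for all patients, is an assumption made here.

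**The plan's own figure.** 85 / (1 − 0.15) = 100. The inflation for drop-out reproduces.

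**True relapse-free proportion**, S(T) = exp(−rate × T):

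- 24 months: exp(−0.14 × 2) = exp(−0.28) = 75.6%
- 48 months: exp(−0.14 × 4) = exp(−0.56) = 57.1%

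**Completers only, 48 months.** Let s be the share of the 15 leavers who had relapsed, and treat the other leavers as relapse-free through month 48. The percentage is (57.1 − 15 × (1 − s)) / 85.

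| Share of leavers relapsed | Calculation | Completers-only result |
|---|---|---|
| 0% | 42.1 / 85 | 49.6% |
| 43% (same as cohort) | 48.6 / 85 | 57.1% (no bias) |
| 75% | 53.4 / 85 | 62.8% |
| 100% (extreme) | 57.1 / 85 | 67.2% |

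At the ends of the protocol's interval for the rate, the true value and the 100% extreme are:

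- rate 0.12: exp(−0.48) = 61.9%, and 61.9 / 85 = 72.8%
- rate 0.17: exp(−0.68) = 50.7%, and 50.7 / 85 = 59.6%

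**Completers only, 24 months.** If 8 patients had left by then, all after a relapse, 75.6 / 92 = 82.2% against a true 75.6%. This too is an extreme.

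**The other two readings, 48 months, exit unrelated to relapse and uniform over 4 years.** The average relapse-free proportion at exit is (1 − 0.571) / 0.56 = 0.766.

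- Leavers without an event counted as relapse-free: (85 × 0.571 + 15 × 0.766) / 100 = 60.0%
- Event-free leavers dropped, relapsed leavers kept: 85 × 0.571 / (85 + 15 × 0.234) = 54.9%
- Completers only: 57.1%, unbiased

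**A mixed pattern, by simulation (400,000 patients).** The assumptions are that 20% of relapsing patients leave soon after the relapse, and that about 7.5% leave for unrelated reasons over 4 years. Total exit is then about 15% and the true value 57.2%.

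| Summary at 48 months | Result |
|---|---|
| Completers only | 62.5% |
| Leavers without an event counted as relapse-free | 58.7% |
| Completers plus known relapsers | 56.2% |
| Kaplan-Meier, relapse kept as event, others censored at exit | 57.2% |

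Completers-only is right under unrelated exit and more than 5 points too high under mixed exit. Each of the other two readings is nearly right when most exits follow a relapse, and 2 to 3 points off when none do.

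**NEDA-3.** The documents give no rate. If all 15 leavers were active, completers-only multiplies the true rate by 100 / 85 = 1.18. For an assumed true rate of 30% to 50%, that shows as 35.3% to 58.8%.

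**The case against.** The strongest reply is that a denominator, a NEDA-3 rule and censoring normally belong in the SAP. The protocol says that one will follow, and it is not shown. That is fair, and the absence of such detail alone would be no finding. What stands is that section 12.2 does state a method, section 12 makes it the basis of the SAP and asks for departures to be justified, and that method combined with 6.3.3 and the planned drop-out gives a result that depends on who left.

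A reader might infer that the protocol orders a complete-case analysis in which known failures are deleted. The text does not say so. In section 12.2 the exclusion of missing values is written only for continuous variables. The ban on replacement rules out imputation, but a recorded relapse is observed data and needs none. Relapses are collected at every visit after the first, and the withdrawal visit schedules relapse, EDSS and MRI. An ordinary reading of relapse-free at 48 months would already count an earlier relapse as failure. The difficulty is that no rule says so, for relapse or for NEDA-3.

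Three further points stand and limit the claim. Completers-only is unbiased if exit is unrelated to activity. Time to first relapse is already an endpoint, so a sound relapse-free estimate is within reach. Shifts of 2 to 3 points are small beside a 95% half-width of about 10 points (1.96 × √(0.571 × 0.429 / 100) = 0.097). Kaplan-Meier also has its own assumption: a relapse-free patient who switches drug because of MRI activity is not censored at random.

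**Conclusion.** The point holds in a limited form. The stated method leaves two quotable proportions dependent on an unstated denominator and on the pattern of exit, and the withdrawal rule makes activity-linked exit plausible. With 15 of 100 leaving and a rate of 0.14, a completers-only figure at 48 months runs from no bias to about 6 points too high if 75% of leavers had relapsed (62.8% against 57.1%), and 10 points at the extreme (67.2%). The other two readings err by 2 to 3 points under unrelated exit, in opposite directions.

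The 67% and 82% figures are bounds and not forecasts: they require every leaver to have relapsed first, while consent withdrawal and loss to follow-up are also listed reasons. Nor do the documents show that the reported proportions will be too high, because the direction depends on the denominator chosen. All relapse figures rest on a constant Poisson rate. The NEDA-3 factor of 1.18 rests on all leavers being active.

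These are descriptive secondary endpoints, and an SAP that is not shown may settle the matter. The change should be made, but it does not touch the primary endpoint.

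**What to change.** In section 12.2, and then in the SAP:

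1. Count a patient as not relapse-free, or not NEDA-3, from the first documented qualifying event onward, including events recorded at the premature withdrawal visit.
2. Censor activity-free patients at their last assessment.
3. Report Kaplan-Meier estimates with 95% CI at 24 and 48 months on all treated patients. The relapse estimate follows directly from the existing time-to-first-relapse endpoint. NEDA-3 needs a matching time-to-first-activity variable.
4. Give the completers percentage as supportive, with its denominator.
5. Because censoring at a switch of drug may be informative, add a sensitivity analysis that counts activity-free patients who leave to start a new disease modifying drug as failures.

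The cost is wording and slightly more analysis work. No assessment is added, since relapse, EDSS and MRI are already in the collection schedule, including at withdrawal. The proportions may move in either direction.

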## 8 DATA COLLECTION

### 8.1 Data source

Patients' medical charts, any relevant diagnostic reports including description of MRI scans recorded as part of the standard of care and number of actually used Cladribine 10 mg tablets for adherence evaluation as described in section 5.1 are the source documents for study data collection. Clinical information recorded in patients' medical charts and/or diagnostic reports will be entered into the eCRF (Electronic case report form).

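### For tablets taken away from the site, adherence rests on packages patients are asked to bring back, with no stated fallback and no record of where the count came from

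*Protocol*

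**What the plan says.** Section 7.2 lists adherence after each dosing period as a secondary endpoint, assessed at 3 and 15 months "by counting used tablets from original packages as patients will be asked to bring them to the site". Table 8-1 repeats the method for the tablet number at V2 and V5, "as counted from original packages brought back to the site", so both courses are covered.

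Section 5.1 describes the procedure: "patients will be asked to bring used/partially used Cladribine 10 mg tablets packages to the next visit after dosing". It adds a condition that Section 7.2 and Table 8-1 omit: the request applies "if Cladribine 10 mg tablets are not administered in the participating site as per standard practice". Section 8.1 names no other source specific to adherence and refers back: "number of actually used Cladribine 10 mg tablets for adherence evaluation as described in section 5.1 are the source documents".

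Section 8.2 collects a planned tablet number at V1 and V4 and a single used-tablet number at V2 and V5. It lists no item for whether packages were returned or how the number was obtained. Section 12.2 states "Missing data will not be replaced", and its summaries of continuous variables leave missing values out of the count.

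Adherence appears in the study title and as an objective in Section 4.2, which also lists its association with relapse.

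**The concern.** Package return is voluntary, and the protocol does not say what happens when a home-dosed patient attends V2 or V5 without packages. Two outcomes are possible. If the method is followed literally, there is no count and the patient leaves the adherence summary and the adherence-relapse analysis. If the physician enters a number from memory, patient report or the chart, it sits in the same field as a true count and cannot be told apart. Site-administered intake goes into that field as well.

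Patients who forget or discard packages may also be those who took tablets less reliably, in which case a summary of counted patients would look too favourable. In the adherence-relapse objective the same patients would be lost or misclassified on the exposure. With about 100 patients, a few lost non-adherent patients could remove much of the contrast that this analysis needs. Without a source item the analyst can neither see the problem nor bound it. The issue concerns patients who remain in the study and attend, and is separate from early withdrawal or not starting the second course.

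**Working it through.** **Plan's own figure.** The protocol gives no adherence level, package return rate or share dosed at the site, so there is nothing to reproduce.

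**Step 1: what each section settles for a patient at V2 or V5.**

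- Dosed at the site: Section 5.1 takes these tablets out of the package request. A used-tablet number is still collected under Section 8.2.
- Dosed at home, packages brought: counted as Sections 5.1 and 7.2 and Table 8-1 describe.
- Dosed at home, no packages: Section 7.2 and Table 8-1 give no value, Section 8.1 refers back to Section 5.1, which offers no alternative, and Section 12.2 does not impute.

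All three cases feed one number per course, with no marker of origin.

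**Step 2: effect on a summary of counted patients.** Section 7.2 sets no threshold for being adherent, so the proportion adherent is used here for illustration. Let m be the share of starters with no count, A_C the proportion adherent among counted patients and A_U that among uncounted patients.

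- Reported = A_C
- True = (1 − m) × A_C + m × A_U
- Reported − true = m × (A_C − A_U)

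The error is positive only if uncounted patients are less adherent, zero if they are equal, and negative if they are more adherent. Patients dosed at the site lower m.

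**Step 3: size over assumed values.** Assume A_C = 95%, m from 5% to 30% and A_U from 60% to 100%. Entries are reported minus true, in percentage points.

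| m | A_U = 100% | 95% | 80% | 60% | Bounds on true adherence |
|---|---|---|---|---|---|
| 5% | −0.25 | 0 | 0.75 | 1.75 | 90.25% to 95.25% |
| 10% | −0.5 | 0 | 1.5 | 3.5 | 85.5% to 95.5% |
| 20% | −1.0 | 0 | 3.0 | 7.0 | 76.0% to 96.0% |
| 30% | −1.5 | 0 | 4.5 | 10.5 | 66.5% to 96.5% |

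Example: m = 10%, A_U = 80% gives 0.10 × (95 − 80) = 1.5 points. The bounds are (1 − m) × 95% if no uncounted patient is adherent and (1 − m) × 95% + m if all are. At m = 10% these are 0.90 × 95 = 85.5% and 85.5 + 10 = 95.5%.

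**Step 4: asymmetry.** At m = 10% the reported 95% could be too high by up to 95 − 85.5 = 9.5 points, but too low by at most 95.5 − 95 = 0.5 points. When counted adherence is near its ceiling, the room for error is mostly on the favourable side. That describes what is possible. It does not show what will happen.

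**Step 5: limit of the calculation.** It applies where the value is missing. If a recalled number is entered, the problem becomes unmarked measurement error, whose size cannot be derived from the protocol.

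**The case against.** The strongest case on the other side has four parts.

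- **Design.** The study is non-interventional and mandates no assessment, so return can only be requested. Asking for packages and comparing the count with a recorded planned number is a reasonable step. This stands: voluntary return is not itself the fault.
- **Data capture.** The items in Section 8.2 carry no condition on package return, medical charts are a general source in Section 8.1, and Section 9.3 allows queries, so a number may be obtained another way. This stands in part. Exclusion is not certain, but a number obtained that way would be unmarked.
- **Other documents.** Denominators and sensitivity bounds are ordinary SAP content, and eCRF instructions are kept separately, so the absence of a source item from Section 8.2 does not prove the eCRF lacks one. This also stands in part. The SAP may settle the analysis, but it cannot recover a source that was never collected, and the protocol fixes both the measurement method and the list of data items.
- **Importance.** Adherence is a descriptive secondary endpoint and the primary annualized relapse rate does not depend on it. This stands and limits the weight of the point.

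A reader might also infer that all tablet use is counted only from returned packages, or that reported adherence is overstated. The documents support neither. Section 5.1 exempts tablets administered at the site. The direction of any error depends on how adherent uncounted patients are, about which the protocol says nothing.

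**Conclusion.** The point holds in a limited form. For tablets not administered at the site, the protocol ties adherence in both courses to packages patients are asked to bring, states no fallback and lists no item for the source of the number. Reported adherence may be biased, plausibly upward if patients without packages are the less adherent ones. Neither direction nor size can be established from the protocol.

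Over the assumed ranges above (95% adherent among counted patients, 5% to 30% without a count, 60% to 100% adherent among those), the error runs from 1.5 points too low to 10.5 points too high. All of these inputs are assumptions. The finding is a cheap improvement to a secondary endpoint that is also a titled aim and the exposure in one objective.

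**What to change.** At V2 and V5, in Section 8.2 and Table 8-1, add one coded item beside the used-tablet number, giving the source of the count: administered at site, packages returned, patient report or chart, or not available. Carry the site-administration exception of Section 5.1 into Section 7.2 and Table 8-1 so that the three places agree.

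In Section 7.2 or 12.2, state that adherence is reported overall and by source among all patients who started the course, with the number in each source category. The start date already collected at V2 and V5 identifies that group. Add a sensitivity bound for each course that counts not-available values as not adherent.

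The cost is one eCRF field at two visits and one extra table, with no added patient procedure. The downside is that the adherence figure may be less favourable or have to be shown as a range.
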